### 2) clinical efficacy evaluation:

- length of hospital stay
- [visual analogue scale](#) (VAS) measurement before and after surgery; duration of surgery.
- SF Rand/ PROMIS preop, 6 weeks and 3 month follow-up.
- Duration of the procedure

### 3) cognitive evaluations

- CAM-ICU/3D-CAM & 3D-CAM-S will be collected preop, during the hospitalization, and 6 weeks and 3 month follow-up
- TICS-m, TMT, COWAT, and BDI preop, 6 weeks and 3 month follow-up.

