#### **Analysis of Secondary End Points:**

1. LOH: LOH will be defined from the day of surgery until the patient is medically ready for discharge. The 'actual LOH' will be defined as the duration from the day of surgery to actual discharge. The discharge will depend on the patient insurance and facility availability. The 'actual LOH' will reflect the duration of hospitalization in the general community, while the LOH will reflect the effect of TXA on improving the postoperative course of the patient. We will test for difference in mean between the 2 groups for both LOH and 'actual LOH'. A multivariable linear regression model will be used to adjust for factors related to longer LOH such as BMI, higher ASA score preoperatively, SF-36/PROMIS, and number of level fused.
2. We will analyze the cost-effectiveness of TXA by computing the cost reduction from the decreased in transfusion and LOH and the cost increase from treating TXA related side-effects: additional thromboembolic complications (cost of diagnosis and treatment). We will test for the difference in the mean between the two groups.
3. The other endpoints (cognitive assessments) are exploratory.

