Cover Page for Statistical Analysis Plan

Sponsor-Investigator:	[name]
NCT Number:	NCT04272606
Unique Protocol ID:	201912099
Official Title:	Prospective, Randomized, Double Blind Study on the Effects of Tranexamic Acid on Intraoperative Blood Loss During Lumbar Spinal Fusion And Instrumentation
Date of Document:	05 December 2023

Statistical Analysis

All analyses will be conducted using R statistical software (version 4.3.1). Continuous variables will be summarized using medians and interquartile ranges and comparisons between groups will be done made using Wilcoxon rank sum or Kruskal-Wallis tests. Pairwise analyses within a group will be made using the Wilcoxon signed rank test. Categorical variables will be summarized using counts and percentages, and comparisons between groups will be performed using Pearson χ^2 test or Fisher exact test. Kendall's tau (τ) will be used as a non-parametric test of association between variables. For all analyses, the threshold for significance will be <0.05 without adjustment for multiple comparisons. Variables will be compared between groups by calculating standardized mean differences.

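### The SAP specifies no baseline-adjusted between-arm analysis for the cognitive, VAS and SF/PROMIS scores, and its within-group tests cannot stand in for one

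*Protocol*

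**What the plan says.** **Data collected.** The Protocol, Outcome assessment, item 3, lists "TICS-m, TMT, COWAT, and BDI preop, 6 weeks and 3 month follow-up". The main Protocol section confirms that the cognitive battery is completed at the preoperative visit and repeated at both postoperative clinic visits. Outcome assessment, item 2, lists "SF Rand/ PROMIS preop, 6 weeks and 3 month follow-up", and VAS before and after surgery.

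**SAP.** The SAP is a single paragraph. For continuous variables, "comparisons between groups will be done made using Wilcoxon rank sum or Kruskal-Wallis tests". Its only paired method is this: "Pairwise analyses within a group will be made using the Wilcoxon signed rank test". It ties neither test to a named outcome and does not say whether a follow-up score or a change score would be ranked. Significance is set at 0.05 with no multiplicity adjustment. Groups are also to be compared by standardized mean differences.

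**Protocol analysis sections.** These add no model that uses an outcome's own baseline. The ANOVA is for blood loss. The regression is for length of hospitalization: "A multivariable linear regression model will be used to adjust for factors related to longer LOH such as BMI". SF-36/PROMIS is one of those adjustment factors, which is its only stated analytic role. On cognition the Protocol says "The other endpoints (cognitive assessments) are exploratory".

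**Endpoint lists.** Exploratory endpoint 4 concerns the effect of delirium on cognition. Follow-up VAS and SF/PROMIS scores are in none of the lists.

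**The concern.** A preoperative score usually predicts the same score after surgery. A between-arm comparison that leaves it out carries avoidable noise, and with about 45 to 50 patients per arm there is little precision to spare. The baseline costs the trial nothing extra, because it is already scheduled.

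The within-group tests raise a separate point. A change from before surgery to 6 weeks or 3 months in one arm reflects the operation, recovery and repeated testing as well as any effect of TXA. Only the contrast between arms isolates TXA. If one arm's change reaches p < 0.05 and the other's does not, that pattern is not evidence of a treatment effect. The SAP neither labels these tests descriptive nor limits what may be concluded from them. Applied by arm to the four cognitive scores and SF/PROMIS, they would number 5 scores × 2 follow-ups × 2 arms = 20, before VAS is counted, each at an unadjusted 0.05.

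**Working it through.** **Inputs.** The Protocol's sample-size section recruits 50 per arm and assumes at least 10% loss, so 50 × 0.9 = 45 per arm. Alpha is 0.05, taken as two-sided. The documents give neither the baseline-to-follow-up correlation r nor a target difference for these scores. Values of r from 0.3 to 0.7 and a difference of 0.5 SD are assumed.

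**The plan's own figure.** There is none for these outcomes. The stated 40 per arm is for blood loss and transfusion. No SD is given with it, so it cannot be checked, and it does not bear on this point.

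**Step 1: precision.** With equal variance at both times, the variance of the arm difference, relative to the follow-up score alone, is:
- follow-up score alone: 1
- change score: 2(1 − r)
- linear ANCOVA on the baseline: 1 − r²

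The equivalent gain in patients is 1/(1 − r²) − 1 against the follow-up score. Against the change score, the variance ratio is (1 − r²)/[2(1 − r)] = (1 + r)/2, so the gain is 2/(1 + r) − 1.

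| r (assumed) | Change score | ANCOVA | Gain vs follow-up score | Gain vs change score |
|---|---|---|---|---|
| 0.3 | 1.40 | 0.91 | 10% | 54% |
| 0.5 | 1.00 | 0.75 | 33% | 33% |
| 0.6 | 0.80 | 0.64 | 56% | 25% |
| 0.7 | 0.60 | 0.51 | 96% | 18% |

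**Step 2: power.** For a 0.5 SD difference and n = 45 per arm, power ≈ Φ(0.5/√(2f/45) − 1.96), where f is the variance factor.
- f = 1: Φ(2.372 − 1.96) = 66%
- f = 0.91 (r = 0.3): 70%
- f = 0.75 (r = 0.5): 78%
- f = 0.51 (r = 0.7): 91%

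**Step 3: validity of the planned between-arm test.** Normal scores were simulated with no treatment effect, 45 per arm, 4,000 runs per setting, r = 0.5 or 0.7, and a common change over time of 0 to 0.5 SD. The rank-sum test rejected in 4.4–5.5% of runs on follow-up scores and 4.6–5.4% on change scores. It holds its level either way.

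**Step 4: comparing two within-arm p-values.** The same simulation counted trials in which exactly one arm had a significant signed-rank test.

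| Common change (SD) | r = 0.5 | r = 0.7 |
|---|---|---|
| 0 | 9% | 9% |
| 0.2 | 38% | 47% |
| 0.3 | 50% | 44% |
| 0.5 | 20% | 3% |

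This agrees with theory. If each arm is significant with probability p, exactly one is significant with probability 2p(1 − p). That is 2 × 0.05 × 0.95 = 9.5% with no change, and at most 50%, when p = 0.5.

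**The case against.** A reader might infer that the SAP replaces the arm comparison with within-arm tests, or that it has decided to ignore baseline between arms. The documents support neither reading. Between-group and within-group tests are both planned, and nothing says that one displaces the other. The SAP is a generic list of methods. It includes Kruskal-Wallis, usually used for three or more groups, so its groups need not always be the two arms. The signed-rank test might be meant for other repeated measures, such as hemoglobin. A rank-sum test on change scores, which is not excluded, would use the baseline.

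The stakes are also limited. The cognitive endpoints are exploratory, VAS and SF/PROMIS follow-up scores are in no endpoint list, and no power target exists for any of them. The listed cognitive endpoint concerns delirium, not treatment arm. The plan never says it will infer an effect from one arm's p-value, so the percentages in step 4 apply only if someone does. The larger gains depend on an assumed high correlation and on a follow-up-only comparator. The factor 1 − r² belongs to linear ANCOVA, so a rank-based version would only approximate it.

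All of this stands as a limit on size. It does not fill the gap: no between-arm analysis adjusted for the preoperative score is specified. If change scores were meant, they gain nothing over the follow-up score until r exceeds 0.5, and ANCOVA has the smaller variance at any r below 1. Standardized mean differences can show a baseline imbalance but do not adjust for it.

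**Conclusion.** The point holds as an omission that costs precision, not as an error in the planned arm comparison. Against the follow-up score alone, the gain forgone is equivalent to 10%, 33% or 96% more patients at r = 0.3, 0.5 or 0.7. Against change scores it is about 33% to 18% for r from 0.5 to 0.7. All of these figures rest on assumed correlations and a linear model, and the power figures also on an assumed 0.5 SD difference.

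The within-group tests are harmless as description but cannot support a treatment-effect claim. With no treatment effect and a common change of 0.2 to 0.3 SD, exactly one arm would be significant in 38–50% of trials. The outcomes affected are exploratory or unlisted, so the primary blood-loss and transfusion conclusions are not touched.

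**What to change.** Add to the SAP:

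1. Wherever TICS-m, COWAT, TMT, BDI, VAS or SF/PROMIS is compared between arms, analyze each follow-up score by ANCOVA on its preoperative value, rank-based if the score is skewed. Report the adjusted difference with its 95% confidence interval, or a rank-based equivalent.
2. Present within-arm changes descriptively, without p-values.
3. Treat the exploratory analysis of delirium and cognition as a separate, non-randomized comparison, also adjusted for the preoperative score.

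The cost is a few sentences in the SAP. The preoperative values are already scheduled, and the Protocol already accepts covariate adjustment for transfusion, blood loss and length of hospitalization. No patients, visits or measurements are added. The wording should be settled before the arms are unmasked; if that has already happened, label the adjusted analyses post hoc.

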### **Venous thromboembolism prophylaxis**

Patients received antithrombotic prophylaxis according to the institutional guidelines and protocols of each participating service and the individual risk estimated by the investigator. The study protocol includes evaluation of the probability that a patient would experience venous thromboembolism (VTE) using the Wells clinical prediction guide for deep venous thrombosis (DVT) and pulmonary embolism (PE) or the Geneva criteria for PE. DVTs are diagnosed by using US and PEs by using CTA. Clinically and radiologically confirmed DVT or PE are considered severe adverse events. LWMH or USQH were used after 24h of the procedure (adjusted to weight and renal function). Patients are mobilized as early as possible with Physical and occupational therapy.

### **Study design:**

**Measures to minimize bias: randomization and blinding:** Randomized block design with variable block sizes will be used to randomize subjects to the 2 groups with a 1:1 ratio. Randomization will be generated by a randomization coding software (SAS Version 9.4). Randomization schema will be distributed to the pharmacy and sequence numbers will be identified to match patient enrollment. We will use triple masking: Concealment of randomization, blinding of treatment (placebo and TXA are indiscernible) and blinding of data analysis. Unmasking will be performed at the end of the trial. We will allow for unplanned masking in case of severe adverse events by the DSMB. (See Adverse events section).

### **Sample Size Determination Based on Primary Endpoint (Blood loss and transfusion)**

We are planning a study of continuous response variable from independent control and experimental subjects with 1:1 allocation ratio. Primary calculations are based on the mean difference from a meta-analysis of RCT studies between patients who received TXA and those who received placebo. The amount of blood loss per patient significantly decreased with TXA with a mean difference (MD) of 681.81 ml (95% CI: 214.49 to 1149.12 ml). The pooled weighted MD for blood transfusion per patient between TXA group and placebo group is -234.61 ml (95% CI: -383.23 to -85.99 ml). However, there was significant heterogeneity within the selected studies. The TXA use could decreased 44% risk of blood transfusion compared with the placebo group with an OR of 0.56 (95% CI: 0.36 to 0.87). Based on the previous studies, we will need to study 40 experimental subjects and 40 control subjects to be able to reject the null hypothesis (i.e. the population means of the experimental and control groups are equal) with a probability of 0.9 (power = 90%) (Table 2). The Type I error probability associated with this test is 0.05. We will thus recruit 50 subjects per group and assume at least a 10% loss to follow-up. thrombosis complications and the use of TXA with an OR of 0.99 (95% CI: 0.06 to 16.07).

### **Sample size calculation for Secondary endpoints:**

1. We do not anticipate any difference in thrombosis complications as a meta-analysis showed an OR of 0.99 (95% CI: 0.06 to 16.07).
2. Analyses for LOH will be based on the difference in mean hospital stay between the 2 groups. This will be adjusted on the number of level fused, presence of a neurological deficit, and BMI
3. Cost effectiveness analysis: The cost of TXA has to be compared with the cost reduction from shorter LOH and reduction in transfusion requirements.

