**Secondary Objectives:**

1. To test the effect of TXA on the following:
  - a. Duration of surgery (Skin to skin)
  - b. Length of hospitalization (LOH)
  - c. Cost/effectiveness analysis
2. To assess the safety of TXA.

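### The expectation of no thrombosis difference rests on an uninformative odds ratio interval, and the safety comparison has a p-value rule but no interval for the difference

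*Protocol*

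**What the plan says.** The protocol's Secondary Objectives include: "To assess the safety of TXA". Its Secondary endpoints make this comparative, naming thromboembolic events and worsening renal function in TXA against placebo. Safety analysis defines renal impairment as a creatinine rise of more than 20% from baseline and plans to compare the frequency and severity of adverse events.

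Item 1 under Sample size calculation for Secondary endpoints reads: "We do not anticipate any difference in thrombosis complications as a meta-analysis showed an OR of 0.99 (95% CI: 0.06 to 16.07". Despite the heading, the item gives no event rate, power, margin or precision.

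The trial is sized on blood loss and transfusion alone: "we will need to study 40 experimental subjects and 40 control subjects to be able to reject the null hypothesis" with 90% power, and then "We will thus recruit 50 subjects per group and assume at least a 10% loss to follow-up".

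The protocol's Analysis of Secondary End Points covers length of hospitalization and cost and gives no method for safety. The SAP names no safety endpoint. Its general rule summarizes categorical variables by counts and percentages and compares them by Pearson chi-square or Fisher exact test. It adds: "For all analyses, the threshold for significance will be <0.05 without adjustment for multiple comparisons". It also mentions standardized mean differences. It specifies no confidence interval for any outcome.

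**The concern.** An odds ratio close to 1 with an interval from 0.06 to 16.07 shows that the source data said almost nothing about thrombosis. It does not show that the arms are alike. The protocol uses it as the reason to expect no difference, and the plan then supplies only a significance test for the comparison.

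At this sample size a non-significant result is the likely outcome under no harm and also under a two- to four-fold increase in a rare event. Without an interval, the report would not show how much harm the data leave open. The answer to the safety objective is at stake; the primary endpoint is not affected.

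**Working it through.** **1. The protocol's odds ratio.** Inputs: 0.99, 95% CI 0.06 to 16.07.
- Geometric midpoint: √(0.06 × 16.07) = 0.98, so the interval is symmetric on the log scale and agrees with the stated estimate to rounding.
- SE of log OR: (ln 16.07 − ln 0.06) / (2 × 1.96) = (2.777 + 2.813) / 3.92 = 1.43.
- Reach: 16.07 upward and 1/0.06 = 16.7 downward.
- For scale, the variance is 1.43² ≈ 2.03. In a single two-by-two table the variance of a log OR is at least 1/a + 1/b, where a and b are the event counts. One event per arm already gives 1 + 1 = 2. If the estimate behaved like one table, it would carry the information of about one event per arm.

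**2. Numbers per arm.** 50 recruited; 50 × 0.9 = 45 after 10% loss; 40 required for the primary endpoint. The 40 is not at issue here.

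**3. Smallest significant split, two-sided Fisher.** For x events against 0 in equal arms, p = 2 × C(n, x) / C(2n, x).
- n = 50, x = 6: 2 × 15,890,700 / 1,192,052,400 = 0.027.
- n = 50, x = 5: 2 × 2,118,760 / 75,287,520 = 0.056.

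| Per arm | 5 v 0 | 6 v 0 |
|---|---|---|
| 50 | 0.056 | 0.027 |
| 45 | 0.056 | 0.026 |
| 40 | 0.055 | 0.026 |

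The 6 v 0 split applies only when placebo has no events. At 50 per arm Fisher needs 8 v 1, 10 v 2 and 14 v 5. Continuity-corrected chi-square also needs 6 v 0 (p = 0.035 at 50 per arm). Uncorrected Pearson is significant at 4 v 0 (p = 0.041), but with an expected count of 2 events in each arm, which is too few for that test.

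**4. Power at 50 per arm.** Summed over two independent binomials. The documents give no event rates, so all rates are assumed.

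| Placebo v TXA | Fisher | Uncorrected Pearson |
|---|---|---|
| 2% v 4% | 0.6% | 5% |
| 2% v 8% | 9% | 26% |
| 10% v 20% | 19% | 30% |
| 2% v 16% | 57% | 74% |
| 10% v 30% | 64% | 73% |
| 2% v 24.7% (OR 16.07) | 92% | 97% |

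The last TXA rate is (0.02 × 16.07) / (0.98 + 0.02 × 16.07) = 0.247. The 10% rows stand for an outcome commoner than DVT or PE, as the creatinine criterion may be.

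**5. Size needed to power this endpoint.** To detect a true OR of 2 with 80% power at two-sided 0.05 takes about 2,398, 1,221 or 516 per arm at assumed placebo rates of 1%, 2% or 5%. Enlarging this trial is not a realistic remedy.

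**6. What an interval would show.** With zero events in an arm of n, the two-sided exact 95% upper limit is 1 − 0.025^(1/n): 7.1% at 50, 7.9% at 45 and 8.8% at 40.

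Take 3/50 v 0/50 as an example. Fisher gives p = 0.24. The risk difference is 6 points. The Wilson limits are 2.1% to 16.2% for 3/50 and 0% to 7.1% for 0/50. Newcombe's score interval is then:
- lower: 0.06 − √[(0.06 − 0.021)² + 0.071²] ≈ −0.02
- upper: 0.06 + (0.162 − 0.06) ≈ 0.16

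The p-value alone reads as no difference. The interval shows that an excess of up to 16 points is not excluded.

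**The case against.** Trials of about 100 patients sized on blood loss are seldom powered for rare harms, and item 1 can be read as explaining why no sample size is given for thrombosis. It sets no equivalence margin and makes no safety claim. This stands as far as power goes, and the point asks for none. It does not rescue the inference from that interval to an expectation of no difference.

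A reader might infer that non-significance is nearly certain whatever the truth. The power table does not support that: very large effects, including the upper limit of the quoted interval at an assumed 2% control rate, would probably be detected.

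A reader might also apply 6 v 0 to every safety outcome. It holds for Fisher with no placebo events. The creatinine criterion may be commoner and would need a different split. The SAP also permits Pearson chi-square and gives no rule for choosing; Fisher is the sensible choice for sparse counts, but that is an inference.

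Nor are p-values the only safety assessment. The Safety analysis section provides for DSMB review, a hold on the study, an independent medical safety monitor and a stopping rule framed as 95% probability, though without a numeric threshold. These govern the conduct of the trial and do not supply the final between-arm estimate. The SAP already plans counts and percentages, and its standardized mean differences are not an interval for a risk difference.

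Finally, neither document says that a null p-value will be taken as proof of safety. The plan leaves that reading open; it does not commit to it.

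**Conclusion.** The point holds in a limited form. The quoted interval does not support an expectation of no thrombosis difference. The only analysis that applies to the comparative safety endpoint is a general test rule with no interval. At 50 per arm Fisher would miss a two-fold rise from 2% more than 99% of the time and a four-fold rise about 91% of the time, so moderate harm from a rare event would usually go undetected.

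This rests on assumed event rates, on two-sided testing, and on the SAP's categorical rule being the one used for safety, which it does not state. It is a weakness in how the safety conclusion would be reached. It is not an error in the trial's sample size, and it leaves the primary analysis untouched. It should be corrected.

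**What to change.** - **Protocol, Sample size calculation for Secondary endpoints, item 1:** replace the expectation with a precision statement. Say that the trial is not sized for thrombosis, and that zero events in an arm would have a two-sided exact 95% upper limit of 7.1% at 50 patients (7.9% at 45, 8.8% at 40).
- **SAP:** name thromboembolic events and creatinine rise above 20% as safety outcomes. To the counts and percentages already planned, add the risk difference with a 95% CI, and name the method in advance (exact or score-based).
- **SAP:** state that the safety conclusion rests on that interval, and that a non-significant test is not evidence of no harm.

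The cost is wording in two places, with no extra patients, visits or data. The safety statement will be less favourable, because the intervals will be wide.

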#### **Analysis of Primary End Point:**

The primary endpoint is the mean difference in total blood loss, intraoperative blood loss and postoperative blood loss. An ANOVA will be used to compare between the 2 groups. A type I error rate of 0.05 will be utilized. An exploratory GLM ANOVA will be used to test for interaction for the subgroups with number of level fused, BMI and duration of surgery.

#### **Analysis of Secondary End Points:**

1. LOH: LOH will be defined from the day of surgery until the patient is medically ready for discharge. The 'actual LOH' will be defined as the duration from the day of surgery to actual discharge. The discharge will depend on the patient insurance and facility availability. The 'actual LOH' will reflect the duration of hospitalization in the general community, while the LOH will reflect the effect of TXA on improving the postoperative course of the patient. We will test for difference in mean between the 2 groups for both LOH and 'actual LOH'. A multivariable linear regression model will be used to adjust for factors related to longer LOH such as BMI, higher ASA score preoperatively, SF-36/PROMIS, and number of level fused.
2. We will analyze the cost-effectiveness of TXA by computing the cost reduction from the decreased in transfusion and LOH and the cost increase from treating TXA related side-effects: additional thromboembolic complications (cost of diagnosis and treatment). We will test for the difference in the mean between the two groups.
3. The other endpoints (cognitive assessments) are exploratory.

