2. LOH

3. Cost effectiveness analysis: cost saving from reduction in transfusion and LOH vs. cost of TXA administration

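### As defined in the protocol, the cost analysis prices the stay to medical readiness rather than to discharge, so the credited saving is off by any between-arm difference in the wait to leave

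*Protocol*

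**What the plan says.** Item 1 of the protocol's Analysis of Secondary End Points sets up two stay variables. For the first, "LOH will be defined from the day of surgery until the patient is medically ready for discharge". The second, 'actual LOH', "will be defined as the duration from the day of surgery to actual discharge". The protocol explains why they can differ: "The discharge will depend on the patient insurance and facility availability". It treats 'actual LOH' as the picture of hospital use in ordinary practice, "while the LOH will reflect the effect of TXA on improving the postoperative course of the patient". Group means are to be compared for both.

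Item 2 of the same section turns to cost: "We will analyze the cost-effectiveness of TXA by computing the cost reduction from the decreased in transfusion and LOH". On the other side of the account it sets the cost of TXA-related side effects, and it compares mean cost between the arms. It does not mention 'actual LOH'.

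The cost analysis appears in two other places, again with LOH alone. Item 3 of the secondary endpoints list has "cost saving from reduction in transfusion and LOH vs. cost of TXA administration". Item 3 of the section on sample size for secondary endpoints has "The cost of TXA has to be compared with the cost reduction from shorter LOH and reduction in transfusion requirements". The SAP mentions neither cost nor length of stay.

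**The concern.** A bed is occupied until the patient leaves, not until the patient is fit to leave. The protocol recognises this by separating the two durations and by naming non-clinical causes of delay. If the cost item follows the definition just above it, the stay component measures clinical recovery rather than bed use.

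Two things follow. Days between readiness and discharge are left out of the stay cost in both arms. Also, a patient who is ready a day sooner but leaves on the same date, because a facility place or an insurance approval sets that date, counts as a saved day although no bed-day was freed. The secondary conclusion on cost could then show a stay saving larger or smaller than the one that occurred, or one that did not occur at all.

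**Working it through.** **Which variable is costed.** Every mention of LOH bears on this.

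| Place in the protocol | How LOH is used |
|---|---|
| Secondary Objectives, item 1b | abbreviation for length of hospitalization |
| Secondary endpoints, item 3 (cost) | LOH, not defined there |
| Sample size for secondary endpoints, item 2 | equated with mean hospital stay |
| Sample size for secondary endpoints, item 3 (cost) | LOH, not defined there |
| Analysis of Secondary End Points, item 1 | defined as surgery to readiness, distinct from 'actual LOH' |
| Analysis of Secondary End Points, item 2 (cost) | LOH, directly after that definition |

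Only one place gives a definition, and the operative cost rule follows it. An analyst who applies the defined term will cost days to readiness.

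**What that does to the comparison.** The plan states no stay, wait, daily cost or expected saving, so there is no figure to reproduce. For each patient:

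actual LOH = LOH + W, where W is the wait from readiness to discharge.

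Means add, and item 2 compares means, so with savings taken as placebo minus TXA:

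- credited saving = mean LOH (placebo) - mean LOH (TXA)
- true bed-day saving = credited saving - D, where D = mean W (TXA) - mean W (placebo)
- error = credited saving - true saving = D

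The wait itself cancels from the contrast. Only its difference between arms remains.

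**Illustration.** Assume a readiness gain of 1.0 day per patient. Both this gain and the values of D are assumptions. The last column scales the error to the 50 patients per group planned in the protocol.

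| D (days) | Credited | True saving = 1.0 - D | Error per patient | Error per 50 TXA patients |
|---|---|---|---|---|
| -0.5 | 1.0 | 1.5 | -0.5 | -25 bed-days |
| 0 | 1.0 | 1.0 | 0 | 0 |
| +0.5 | 1.0 | 0.5 | +0.5 | +25 bed-days |
| +1.0 | 1.0 | 0 | +1.0 | +50 bed-days |

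The +1.0 row is the case where discharge dates do not move at all: the whole readiness gain becomes extra waiting. The +0.5 row is what results if half the patients leave a day earlier and the other half leave on the same date as before (0.5 × 0 + 0.5 × 1.0 = 0.5 day of extra wait). To turn any row into money, multiply by a daily bed cost, which the documents do not give.

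**The case against.** The strongest reply is that LOH is not a strict term in this protocol. The objectives expand it as length of hospitalization. In the sample size section, the cost line comes straight after a line that treats LOH as hospital stay. The authors may well have meant actual stay throughout. This stands as a point about intent, and it rules out saying that they chose to ignore discharge delays. It does not settle what will be computed, because the only definition given says readiness and nothing tells the analyst to depart from it. The same edit is needed on either reading.

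Second, costing to readiness can be defended. If waits are non-clinical and unrelated to when a patient becomes ready, randomisation makes expected waits equal, and the readiness contrast estimates the same saving with less noise. That is correct under its condition. The plan does not state the condition, though, and a discharge date fixed by a facility or an insurer would break it. Whether that happens here is also not documented.

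Third, since both durations will be compared, a readiness gain without a discharge gain would be visible in the results. This lowers the risk of being misled but does not correct the cost figure.

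A reader might infer more than the text supports, in two ways. One is that the saving from TXA must be overstated. The identity shows that the error can be zero or negative, and no document figure points to a direction. The other is that the bias equals the omitted wait multiplied by the daily rate. That product understates each arm's total cost, but it drops out of the contrast when mean waits are equal.

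**Conclusion.** The point holds as a mismatch between a defined term and its use. Under the protocol's own definitions, item 2 costs the stay to readiness, and the days from readiness to discharge are priced in neither arm. The error in the stay saving is the between-arm difference in mean wait, with its sign. Its size cannot be derived from the documents. With an assumed readiness gain of 1 day and D from -0.5 to +1.0, the true saving runs from 1.5 days down to 0, against 1.0 day credited.

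This rests on two things: that the definition in item 1 governs item 2, and that the stay is meant to be valued by bed-days used. The plan states no costing perspective, so the second is an assumption, though a natural one for a saving set against the cost of giving the drug. The consequence is confined to one component of a secondary endpoint. It is worth correcting before analysis, but it touches neither the blood loss and transfusion conclusions nor the safety comparison.

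**What to change.** In Analysis of Secondary End Points, item 2, state that the stay is costed with 'actual LOH' as the base case, and that LOH to medical readiness is a sensitivity analysis showing the potential saving if discharge followed readiness. For consistency, make the same change in the cost line of the secondary endpoints list and in the cost line of the section on sample size for secondary endpoints.

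The edit is a few words in three places and needs no new data, because both durations are already to be compared. It also removes the need to assume equal waits. The drawback is that 'actual LOH' is likely to be noisier, since it adds variation in the wait, so the interval on the cost difference may widen somewhat.
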